Phase 1: Optimization of measurement time and software settings of the dry electrode cap EEG in a non-emergency setting in patients in whom a regular EEG is/will be performed for standard medical care.

Phase 2: Optimization of measurement time and software settings of the dry electrode cap EEG in patients close to our target population in a non-emergency setting.

Phase 3: Validation of several existing algorithms and development of one or more new algorithms for LVO-a detection, as well as optimization of logistics and software settings of the dry electrode EEG cap in patients close to our target population in an in-hospital emergency setting.

Phase 4: Validation of several existing algorithms and algorithms developed in phase 3 for LVO-a detection in patients with a suspected AIS in the ambulance, as well as assessment of technical and logistical feasibility of performing EEG with dry electrode caps in patients with a suspected AIS in the ambulance.

STUDY POPULATION

Phase 1: Patients in the outpatient clinic of the Clinical Neurophysiology department of the AMC, in whom a regular EEG has been/will be performed for standard medical care.

Phase 2: Patients with an AIS admitted to the Neurology ward of the coordinating hospital with an LVO-a (after reperfusion therapy).

Phase 3: Patients with a suspected AIS in the emergency room (ER) of the coordinating hospital (before reperfusion therapy).

Phase 4: Patients with a suspected AIS in the ambulance.

INTERVENTION

Performing a dry electrode cap EEG (in phase 1 in the outpatient clinic, in phase 2 during hospital admission, in phase 3 in the ER and in phase 4 in the ambulance).

MAIN END POINTS

- Primary end point: the area under the receiver operating characteristics (ROC) curve of the theta/alpha ratio for diagnosis of LVO-a, based on dry electrode EEG performed by paramedics in the ambulance in suspected AIS patients;
- Secondary end points:

- Sensitivity, specificity, positive predictive value (PPV) and negative predictive value (NPV) of the theta/alpha ratio, and test characteristics of other existing EEG data based algorithms for LVO-a detection (e.g. Weighted Phase Lag Index, delta/alpha ratio);
- Logistical and technical feasibility of paramedics performing dry electrode cap EEG in the ambulance in suspected AIS patients ;

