3. STUDY DESIGN

The ELECTRA-STROKE is an investigator-initiated, diagnostic study, that consists of four phases (see below).

STUDY PHASE 1: OPTIMIZING MEASUREMENT TIME, SOFTWARE SETTINGS AND DATA TRANSFER LOGISTICS IN PATIENTS IN WHOM A REGULAR EEG HAS BEEN/WILL BE PERFORMED FOR STANDARD MEDICAL CARE IN A NON-EMERGENCY SETTING

This phase will be carried out in the outpatient clinic of the department of Clinical Neurophysiology of a single center (Amsterdam UMC, location AMC). We will perform dry electrode cap EEGs on patients in whom a regular EEG has been/will be performed for standard medical care. We will compare the regular EEG to the dry electrode cap EEG and this way try to optimize the dry electrode cap EEG measurement, software settings, data transfer logistics and measurement time in a population of patients less vulnerable than our target population, in a non-emergency setting.

STUDY PHASE 2: OPTIMIZING MEASUREMENT TIME, SOFTWARE SETTINGS AND DATA TRANSFER LOGISTICS IN PATIENTS CLOSE TO TARGET POPULATION IN A NON-EMERGENCY SETTING.

This phase will be carried out in the brain care unit of a single center (Amsterdam UMC, location AMC). We will perform dry electrode cap EEGs in a population close to our target population – patients that have been admitted with an AIS and an LVO-a – in a non-emergency setting. We will test technical feasibility of the dry electrode cap EEG in patients that are, in part, unable to cooperate with the procedure (e.g. patients that because of lowered consciousness or agitation will not keep their head still).

STUDY PHASE 3: VALIDATION OF EXISTING ALGORITHMS AND DEVELOPMENT OF NEW ALGORITHM(S) IN PATIENTS IN THE EMERGENCY ROOM

This phase will be carried out in the ER of a single center (Amsterdam University Medical Centers, location AMC). In this phase, we will perform dry electrode cap EEGs in patients that are presented to the ER of the coordinating hospital with a clinically suspected AIS, according to the paramedic that presents the patient, or with a known LVO-a. The last category of patients have undergone an initial work-up in a primary stroke center, where the diagnosis LVO-a has been made, and are transferred to our hospital to undergo EVT. The EEG data of this 'enriched' population, with a higher incidence of LVO-a compared to the primary target population, will be used to validate several existing algorithms and to develop one or more new algorithms for diagnosis of LVO-a.

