STUDY PHASE 4: VALIDATION OF ALGORITHMS IN THE AMBULANCE

This phase is the only multi-center phase of this study. It will be carried out in the ambulances of one ambulance station in Amsterdam and one ambulance station in Alkmaar. These ambulances bring patients with a suspected acute stroke to the following hospitals: AMC, VUMC and OLVG West and Noordwest Ziekenhuisgroep, location Alkmaar. These will therefore be the centers participating in this study phase, as well as the Ambulance Amsterdam. The EEG data will be used to validate several existing algorithms (among which is the Brain Symmetry Index) and the algorithm(s) developed in phase 3. Technical and logistical feasibility of performing ambulant EEGs in patients with a suspected AIS in the ambulance will also be assessed.

Phase 4 will start with a 'run in' phase. The objective of this phase is to assess technical and logistical feasibility of performing ambulant EEGs in patients with a suspected AIS, before commencing inclusion of the prespecified study population. Inclusion will not be consecutive at this stage.

The four phases will not necessarily run consecutively; they may also, in part, run simultaneously. Each phase consists of performing a single dry electrode cap EEG per patient and collecting information on patient characteristics, medical history, medication use, physical and neurological examination performed by the treating physician, imaging studies, diagnosis and treatment as well as logistical and technical information, obtained from the patient, the Emergency Medical Service (EMS) and the treating physician. There are no follow up visits. The study will run until the number of patients required according to the sample size calculation have been included for each phase.

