For study phase 4, where we aim to validate existing algorithms and one or more new algorithms for LVO-a detection, our primary outcome measure is the specificity of the dry electrode cap EEG in a population of patients with a suspected AIS. Sample size calculation is based on an expected specificity of 70% for LVO-a. Originally, sample size calculation was based on an expected LVO-a rate of 7% and a dropout rate of 20%. However, an interim analysis, based on 137 suspected stroke patients in whom an EEG was performed in the ambulance, showed an actual incidence of LVO-a of 5% and a dropout rate of 58%. Patients considered as a 'drop out' had insufficient EEG data quality (n=72), onset of symptoms >24 hours before EEG registration (n=4) or did not give consent for participation in the study (n=3). The EEG data quality increased over the course of the study, so we expect a lower dropout rate for future EEG registrations. Based on these interim data, we adjusted the sample size for phase 4 of the study as follows.

With an incidence of LVO-a of 5% among patients with a clinically suspected AIS in the ambulance, an alpha of 0.05, and a maximum margin of error of 7%, 174 patients with a suspected AIS are required²¹. Assuming a dropout rate of 55%, we intend to recruit 386 patients with a suspected AIS. A patient is considered a 'drop out' if no informed consent is/can be obtained, if no information on the diagnosis made by the treating physician is/can be obtained, or if the EEG measurement is of insufficient technical quality, as judged by the clinical neurophysiologist. Patients included in the 'run in' phase are excluded from the primary analysis and thus not included in our sample size calculation. In the 'run in' phase, we will additionally include 50 patients or less.

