8. METHODS

8.1 STUDY PARAMETERS/END POINTS

8.1.1 MAIN STUDY PARAMETER/END POINT

The primary end point of the study is the area under the ROC curve of the theta/alpha ratio for diagnosis of LVO-a, based on dry electrode EEG performed by paramedics in the ambulance in suspected AIS patients.

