10. STATISTICAL ANALYSIS AND ALGORITHM DEVELOPMENT

STUDY PHASE 1 AND 2

For phase 1 and 2 of this study, the obtained data will not be statistically analyzed, for these phases are meant to gain technical and logistical information on the products being used in a non-emergency setting.

STUDY PHASE 3

For phase 3 of this study, we will determine the diagnostic accuracy of several existing and one or more self-developed EEG data based algorithms for LVO-a detection by comparing the proportions of patients with and without an LVO-a as predicted by EEG to the proportion of patients with and without an LVO-a as diagnosed by the treating physician. A receiver operating characteristic (ROC) curve will be plotted for each algorithm and the optimal cut-off value for each algorithm will be determined. For these cut off values, the sensitivity, specificity, negative predictive value and positive predictive value will be reported with 95% confidence intervals.

ALGORITHM DEVELOPMENT

Data of phase 3 and phase 4 will be used to develop one or more new EEG based algorithms for LVO-detection. We will create artificial intelligence (AI) based algorithm(s). First, we will create a logistic

regression model based on standard EEG features, e.g. time domain characteristics, power spectral density in different frequency bands, coherence measures, and entropy measures. This will be the reference to assess the improvement of the novel AI based models. Second, we will work on EEG classification algorithms based on random forests and support vector machines, using the same EEG features as input. Finally, to support future studies, we will explore new methods that use raw EEG data as input, such as convolutional or recurrent neural networks³³⁻³⁵.

STUDY PHASE 4

For phase 4 of this study, we will determine the diagnostic accuracy of several existing and one or more self-developed EEG data based algorithms for LVO-a detection by comparing the proportions of patients with and without an LVO-a as predicted by EEG to the proportion of patients with and without an LVO-a as diagnosed by the treating physician. An ROC curve will be plotted for each algorithm and the optimal cut-off value will be determined. For this cut off value, the sensitivity, specificity, negative predictive value and positive predictive value will be reported with 95% confidence intervals.

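### Section 10 uses phase 4 data both to develop the new algorithms and to report their ambulance accuracy, with no separation of training and test patients

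*Combined protocol and SAP*

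**What the plan says.** The Summary defines phase 4 as "Validation of several existing algorithms and algorithms developed in phase 3 for LVO-a detection in patients with a suspected AIS in the ambulance". Section 3 agrees: the phase 3 EEG data "will be used to validate several existing algorithms and to develop one or more new algorithms for diagnosis of LVO-a", and the phase 4 data serve to validate existing algorithms "and the algorithm(s) developed in phase 3".

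Section 10 differs. Under algorithm development it states: "Data of phase 3 and phase 4 will be used to develop one or more new EEG based algorithms for LVO-detection". The methods listed are a logistic regression on standard EEG features, then random forests and support vector machines on the same features, and finally exploratory neural networks on raw EEG. Of the logistic model it says: "This will be the reference to assess the improvement of the novel AI based models".

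The phase 4 paragraph of section 10 then reports accuracy for existing and self-developed algorithms alike. It plots ROC curves, finds an optimal cut-off, and gives sensitivity, specificity and predictive values at that cut-off with 95% confidence intervals.

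Section 3 adds on timing: "The four phases will not necessarily run consecutively; they may also, in part, run simultaneously". Section 8.1.1 fixes the primary end point: "The primary end point of the study is the area under the ROC curve of the theta/alpha ratio for diagnosis of LVO-a". Novel algorithms are a secondary matter (sections 2 and 8.1.2).

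**The concern.** A patient whose data shaped a model cannot also serve as an independent test of it. Section 10 gives phase 4 patients both roles and states nothing that keeps the roles apart: no hold-out set, cross-validation, bootstrap correction, model lock or order of steps. Calendar time does not protect the test, since the phases may overlap. Nor does the blinding in section 8.2, which covers the clinical team and paramedics but not the people building the algorithms.

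Two results are at stake. The first is the phase 4 accuracy of the self-developed algorithms, which readers would take as validation in the ambulance. The second is the comparison of AI models with the logistic reference: if it uses training data, it favours whichever learner overfits most.

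A lesser point is that phase 3 accuracy of the self-developed algorithms is also reported without correction for optimism.

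**Working it through.** **1. Sizes.** Section 4.4 gives phase 3 as 300 patients or fewer, about 60 with LVO-a and 240 without. For phase 4 it assumes specificity 70%, margin of error 7%, alpha 0.05 and LVO-a incidence 5%.

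- Patients without LVO-a: 1.96² × 0.70 × 0.30 / 0.07² = 164.6.
- Evaluable patients: 164.6 / 0.95 = 173.3, rounded up to 174. This matches the plan.
- Recruited: 174 / 0.45 = 386.7, against 386 in the plan, a rounding difference only.
- LVO-a among those evaluable: 174 × 0.05 = 8.7, so about 9 with LVO-a and 165 without.

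**2. Inflation for a logistic model.** Simulation assumptions: normal features, any signal spread over 5 of them, both phases from the same distribution, unpenalised logistic regression, 1000 replicates. Each cell gives mean phase 4 AUC with phase 4 in the training data, then with the model locked on phase 3, then the difference.

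| Best attainable AUC | 10 features | 20 features | 40 features |
|---|---|---|---|
| 0.50 (noise) | 0.617 − 0.503 = 0.11 | 0.657 − 0.497 = 0.16 | 0.731 − 0.500 = 0.23 |
| 0.70 | 0.726 − 0.670 = 0.06 | 0.746 − 0.644 = 0.10 | 0.795 − 0.617 = 0.18 |
| 0.80 | 0.814 − 0.780 = 0.03 | 0.829 − 0.761 = 0.07 | 0.860 − 0.729 = 0.13 |

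The Monte Carlo standard error of each difference is at most 0.002. A variant with ridge-penalised models (300 replicates) agrees: 0.11 to 0.24 with noise, and 0.04 to 0.15 at a true AUC of 0.75.

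**3. Comparison with the logistic reference.** 20 features, best attainable AUC 0.80, phase 4 in training, 60 replicates for the two AI learners.

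| Model | Reported phase 4 AUC | AUC in new patients |
|---|---|---|
| Logistic | 0.83 | 0.77 |
| Support vector machine | 0.99 | 0.73 |
| Random forest | 1.00 | 0.71 |

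Apparent gain over the reference: 0.99 − 0.83 = 0.16 and 1.00 − 0.83 = 0.17. Actual difference: 0.73 − 0.77 = −0.04 and 0.71 − 0.77 = −0.06. With pure noise the forest still scores 1.00 in training (0.50 when locked on phase 3) and the support vector machine 0.99 (0.49 when locked).

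**4. What locking costs in accuracy.** At best attainable AUC 0.80, true AUC in new patients for pooled minus locked training is 0.785 − 0.781 = 0.004 (10 features), 0.770 − 0.761 = 0.009 (20) and 0.742 − 0.728 = 0.014 (40).

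**5. Precision of a locked test.** Hanley-McNeil variance with n₁ = 9 and n₀ = 165: [A(1−A) + (n₁−1)(A/(2−A) − A²) + (n₀−1)(2A²/(1+A) − A²)] / (n₁n₀).

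- A = 0.70: (0.210 + 0.388 + 14.181) / 1485 = 0.00995; SE 0.100; half-width 1.96 × SE = 0.196.
- A = 0.80: (0.160 + 0.213 + 11.662) / 1485 = 0.00810; SE 0.090; half-width 0.176.

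**The case against.** The strongest reply is that the leak is inferred. Section 10 never says that a model trained on phase 4 patients will be scored on those same patients. Read with the Summary and section 3, it could mean that phase 3 models are tested in phase 4 and pooled development follows. The secondary objective of developing algorithms with ambulant EEG (sections 2 and 8.1.2) could explain why phase 4 data are used at all. That reading is possible, but no sentence sets the order, and the objective does not say how the same patients can also be the test set. What is certain is the contradiction and the missing separation; whether leakage would occur depends on the unstated order.

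A second reply concerns the figures. Near-perfect forest and support vector machine values are training-data scores, the worst case. The finding that these models are truly worse than logistic regression rests on a simulated linear signal; with non-linear signal the true ranking could reverse. Phase 3 may also stop short of 300. These points stand. They limit the size and the true ranking, not the direction of the bias.

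A third reply is that section 4.4 calls specificity the primary outcome of phase 4, so the primary analysis may not be clear of the problem. The exemption given here rests on the Summary and section 8.1.1, and the conflict with section 4.4 needs its own correction. The exemption also covers the AUC only. Section 10 finds the cut-off in phase 4 itself, which flatters sensitivity and specificity even for fixed indices: at AUC 0.75 with 9 cases, the simulated Youden index is about 0.50 against a true 0.37.

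**Conclusion.** The concern holds and should be fixed. Section 10 contradicts the design text and permits training performance to be presented as ambulance validation. Under the stated assumptions, the inflation for a logistic model runs from 0.03 to 0.23 in AUC, depending on feature count and true signal. It is larger for flexible learners, enough to make them look better than the reference when they are not. The feature counts, signal strengths, linear signal and exchangeable phases are assumptions.

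The damage is confined to secondary results for the self-developed algorithms. The theta/alpha ratio and the other fixed indices have no trained parameters, so their AUCs do not carry this bias.

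**What to change.** Amend section 10 as follows.

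1. Develop the algorithms to be validated in phase 4 on phase 3 data only. Lock features, model and cut-off before any phase 4 EEG feature is analysed against LVO-a status, and apply the locked algorithms once to phase 4.
2. State what was linked at "an interim analysis, based on 137 suspected stroke patients in whom an EEG was performed in the ambulance". That look used LVO-a status and EEG quality; the text does not say whether EEG features were set against LVO-a. Of the 137 patients, 72 + 4 + 3 = 79 dropped out, leaving 58. If features were analysed against LVO-a, exclude those patients from the locked test or report it with and without them.
3. Compare AI models with the logistic reference only on locked phase 4 results or cross-validated results.
4. Report phase 3 performance by nested cross-validation or bootstrap optimism correction.
5. Keep a pooled phase 3 and 4 refit as a separate development step for future studies, with cross-validated performance only and not called validation.

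Nested resampling of the pooled data would also remove the leak. The locked test is preferred because it is what the Summary and section 3 already describe.

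The cost is wording and resampling code, with no extra patients. The locked models give up training on about 9 LVO-a and 165 other ambulance recordings. The simulated loss in true AUC is 0.004 to 0.014 if the phases are exchangeable. It could be larger if ambulance EEG differs, since phase 3 is enriched and a phase 3 subgroup uses other electrodes and another amplifier (section 7.1). The pooled refit still uses those recordings. The locked test will be imprecise, with a 95% half-width of about 0.18 to 0.20 in AUC, and the report should say so.

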4.4 SAMPLE SIZE CALCULATION

STUDY PHASE 1

For study phase 1, where we aim to optimize measurement time, software settings and data transfer logistics in patients in the outpatient clinic of the Clinical Neurophysiology department of the AMC, we

plan to include 20 patients or less, depending on the judgement of the investigators of when the optimal settings and logistics have been found.

STUDY PHASE 2

For study phase 2, where we aim to optimize measurement time, software settings and data transfer logistics in a population of patients with an AIS in a non-emergency setting, we plan to include 20 patients or less, depending on the judgement of the investigators of when the optimal settings and logistics have been found.

STUDY PHASE 3

For study phase 3, where we aim to validate existing algorithms and to develop one or more new algorithms, we plan to include 60 patients with an LVO-a. Because the coordinating center, where this phase will be conducted, is the only hospital in its region performing EVT, many patients with an LVO-a are transported here. In the population of suspected ischemic stroke patients in this hospital's ER, including patients transferred for EVT, the incidence of LVO-a is approximately 20% based on data from our own stroke database. Therefore, we aim to include 300 patients in this phase (approximately 60 patients with an LVO-a and 240 patients without an LVO-a) or less, depending on the judgement of the investigators of when the goal of this study phase is achieved.

STUDY PHASE 4

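### The self-developed algorithms have no internal validation or reserved test set: phase 3 accuracy is reported in the patients used to build them, and phase 4 is also development data

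*Combined protocol and SAP*

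**What the plan says.** Section 3 gives phase 3 two tasks. Its EEG data "will be used to validate several existing algorithms and to develop one or more new algorithms for diagnosis of LVO-a". Section 4.4 plans the size: "we aim to include 300 patients in this phase (approximately 60 patients with an LVO-a and 240 patients without an LVO-a) or less".

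Section 10, under study phase 3, then reports on the new algorithms in that phase: "For phase 3 of this study, we will determine the diagnostic accuracy of several existing and one or more self-developed EEG data based algorithms". An ROC curve is drawn for each algorithm, an optimal cut-off is picked from it, and sensitivity, specificity, PPV and NPV at that cut-off are given with 95% confidence intervals.

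The algorithm development part of section 10 widens the development set: "Data of phase 3 and phase 4 will be used to develop one or more new EEG based algorithms for LVO-detection". A logistic regression on standard EEG features comes first, and of this model the plan says "This will be the reference to assess the improvement of the novel AI based models". Next come "EEG classification algorithms based on random forests and support vector machines, using the same EEG features as input". Neural networks on raw EEG are to be explored last, in support of future studies.

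The Summary and section 3 describe phase 4 as validation of the algorithms developed in phase 3. Section 10 repeats the phase 3 procedure for phase 4, including the choice of an optimal cut-off.

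No section mentions a data split, cross-validation, bootstrap, optimism correction or a step that freezes the models.

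**The concern.** A model scored in the patients it was fitted to looks better than it is, and the excess grows with its flexibility. Choosing the cut-off in the same patients adds to this, and an ordinary 95% interval around the resulting sensitivity and specificity does not account for either step.

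The comparison with the logistic benchmark is exposed in a particular way. A fully grown random forest reproduces its own training labels almost perfectly, and a logistic model does not. If improvement is judged in the development patients, the more flexible model looks better whether or not it detects LVO-a better.

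A separate test set would settle the matter, and phase 4 appears to be one. But section 10 also lists phase 4 as development data and re-optimises the cut-off in it. Section 3 allows the phases to overlap in time, and nothing says when models become fixed. As written, no set of patients is clearly kept for testing.

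Developing algorithms of optimal accuracy is a declared secondary objective and end point (sections 2 and 8.1.2), so these figures will be read as results.

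**Working it through.** **Planned numbers.**

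- Phase 3 (section 4.4): 60 patients with LVO-a at the stated rate ("the incidence of LVO-a is approximately 20% based on data from our own stroke database") give 60 / 0.20 = 300, hence 240 without LVO-a. This matches the plan.
- Phase 4 (section 4.4): expected specificity 70%, margin 7%, alpha 0.05, incidence 5%. Patients without LVO-a: 1.96² × 0.70 × 0.30 / 0.07² = 164.6. Total: 164.6 / 0.95 = 173.3, rounded up to 174. This also matches.
- LVO-a patients expected among those 174: 174 × 0.05 = 8.7, about 9.

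**Size of the optimism in phase 3.** The documents give neither the number of features nor the strength of signal, so both are assumed. Each run simulates 60 patients with and 240 without LVO-a and independent normal features. There is either no signal, or a modest one (3 features shifted by 0.5 SD). The models are logistic regression, a radial-kernel least-squares support vector machine, and a forest of 100 fully grown trees. The table gives the mean AUC over 12 repeats, in the development patients / in 2,000 new patients.

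| Signal | Features | Logistic | Support vector | Forest |
|---|---|---|---|---|
| none | 10 | 0.63 / 0.49 | 0.98 / 0.50 | 1.00 / 0.50 |
| none | 20 | 0.68 / 0.51 | 1.00 / 0.50 | 1.00 / 0.51 |
| none | 40 | 0.76 / 0.50 | 1.00 / 0.50 | 1.00 / 0.50 |
| modest | 10 | 0.76 / 0.70 | 0.97 / 0.66 | 1.00 / 0.65 |
| modest | 20 | 0.80 / 0.68 | 1.00 / 0.66 | 1.00 / 0.64 |
| modest | 40 | 0.84 / 0.64 | 1.00 / 0.64 | 1.00 / 0.61 |

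With 60 features and no signal, a further set of runs puts the logistic same-patient AUC at 0.82.

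**Apparent improvement when there is none.** With no signal, forest minus logistic in the development patients runs from 1.00 − 0.76 = 0.24 (40 features) to 1.00 − 0.63 = 0.37 (10 features). In new patients both are at about 0.50.

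**Does resampling remove it?** Ten-fold cross-validated AUC with no signal was 0.49 to 0.51 for the logistic and support vector models. With the modest signal it was 0.64 to 0.72, against 0.64 to 0.70 in new patients. So it largely does.

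**How much could phase 4 correct?** Assume a true AUC of A = 0.80 with 9 patients with and 165 without LVO-a. The Hanley–McNeil terms are A / (2 − A) = 0.667 and 2A² / (1 + A) = 0.711. The variance is [0.80 × 0.20 + 8 × (0.667 − 0.64) + 164 × (0.711 − 0.64)] / (9 × 165) = 0.0081. The standard error is 0.09 and the 95% interval about ± 0.18. Even an untouched phase 4 would be imprecise.

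**The case against.** The strongest reply is that the plan is silent on resampling and does not rule it out. The analysts may intend cross-validation, and a random forest supplies out-of-bag predictions without extra planning; with no signal these gave an AUC of 0.49, as they should. That is fair as a statement of what could happen. It does not remove the gap: the plan specifies model families, ROC curves, cut-offs and intervals, and followed literally it reports same-patient accuracy. Cross-validation with feature selection, tuning or cut-off choice left outside the loop would still be optimistic.

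A second reply is that phase 4 validates the algorithms. The Summary and section 3 say so, but section 10 undoes it by feeding phase 4 into development and choosing the cut-off again.

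A reader might infer more than the documents support:

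- *That the machine-learning models are compared with the logistic reference in phase 3, on training data, so that the most flexible wins by construction.* The sentence names no data set. The result follows only if same-patient performance is used.
- *That a wrong algorithm will be carried into the ambulance.* No choose-one rule is stated. Sections 3 and 10 let several algorithms go forward and plot a curve for each.
- *That a phase 3 paper will carry the inflated figures.* Section 12.5 mentions only a final report with any publications.
- *That logistic regression is truly the better model here.* In the table it equals or beats the others in new patients under the modest signal, but that signal was assumed linear. With an assumed difference in variance in 3 of 20 features, AUC in new patients was 0.50 for logistic and 0.80 for the forest. Only the same-patient inflation is robust.

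**Conclusion.** The point holds as a defect in the validation plan for the self-developed algorithms. The phase 3 patients build the algorithms, set the cut-offs and supply the reported accuracy with no correction, and phase 4 is not clearly kept apart. If section 10 is followed as written, a model with no diagnostic value would show a same-patient AUC of about 0.63 to 0.82 (logistic) or about 1.00 (forest). Those sizes rest on the planned 60/240 split, an assumed 10 to 60 features and, for the forest, fully grown trees. Fewer features or stronger regularisation would shrink them. Whether the comparison with the logistic reference is distorted depends on the data in which it is made, which the plan leaves open.

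The primary end point is untouched: the theta/alpha ratio is an existing index and is not fitted by these models. The change should be made, but the main result of the trial does not depend on it.

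**What to change.** In section 10:

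1. Report the phase 3 accuracy of every self-developed algorithm, the logistic reference included, only from patient-level nested cross-validation, with the same folds for all models and with feature selection, tuning and cut-off choice inside the loop. An equivalent bootstrap optimism correction that repeats all these steps would also serve.
2. Define improvement as the paired difference in validated AUC from the logistic reference, with a 95% interval.
3. Lock the models and cut-offs developed in phase 3 before any phase 4 data are used, and evaluate them once in phase 4 at those cut-offs.
4. Label any later refit on pooled phase 3 and phase 4 data as exploratory, and validate it internally in the same way.
5. Reconcile the validation role given to phase 4 in the Summary and section 3 with its development role in section 10.

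The cost is wording, computing time and a little more analysis work, with no extra patients. The reported accuracy will be less favourable, and the single phase 4 evaluation will remain imprecise with about 9 LVO-a patients.
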